2.4.5.2 Secondary Outcome Measures

Secondary outcome measures include:

1. Change in spontaneous pain intensity (measured on 0-10 NRS) from baseline to 60-120 minutes after ondansetron IV infusion, compared between two sessions with and without tariquidar. The pain severity values obtained at 60, 90, and 120 minutes will be averaged to derive the secondary outcome measure. The values will be compared via paired t-test (or Wilcoxon signed-rank test, if data not normally distributed).
2. Changes in NPSI total score and sub-scores (burning pain, paroxysmal pain, paresthesia/dysesthesia score) will be compared between treatment sessions;
3. The association between baseline Conditioned Pain Modulation (CPM) magnitude (Δ CPM) and the % pain reduction from baseline will be determined by bivariate regression. A significant association between the two measures will be indicative of differential analgesic response as a function of descending pain modulation;

Exploratory analyses will be performed to determine if variables such as sex, weight, baseline wind-up ratio (WUR), peak ondansetron plasma concentration, and P-glycoprotein genotype affect the difference in pain reduction between the two study sessions.

A population PK approach will be used to model CSF concentrations of ondansetron with and without tariquidar co-administration.

Table 1. Study Day Timeline

	Drug	Blood*		PK		NRS	NPSI	CPM	WUR	QST	Questionnaires
Screening	TQD	OND	X	Blood	CSF	X	X	X	X	X	X
Study day (min after ondansetron infusion start)											
Baseline			X	X		X	X	X	X	X	
-30 min	TQD / placebo Infusion										
0 min		OND infusion		X		X					
10 min						X					
15 min				X							
20 min						X					
30 min				X	X**	X					
40 min						X					
50 min						X					
60 min				X		X					
70 min							X				
75 min						X					
90 min				X		X					
105 min						X		X	X		
120 min				X		X					
135 min						X					

150 min						X					
165 min						X					
180 min				X		X					
240 min				X		X					
Hourly after discharge- study day						X					
Post-study day (weeks)											
1						daily					
2						daily					
3			X			daily					

*Blood sample = baseline troponin, comprehensive metabolic panel (CMP) and complete blood count (CBC) at the screening visit, a sample prior to visit #2 (3-weeks after treatment #1), and 3 weeks after treatment #2. An additional blood sample will be obtained for genetic analysis for P-glycoprotein polymorphisms on the first study day; TQD=tariquidar; OND=ondansetron; NRS=numerical rating scale; NPSI=neuropathic pain symptom inventory; CPM=conditioned pain modulation; WUR=wind-up ratio; PK – blood samples for ondansetron pharmacokinetics; QST=quantitative sensory testing.

** CSF sample can be obtained anywhere between 30 and 180 minutes after start of ondansetron infusion.

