On each of the intervention dates, women of childbearing potential will undergo urine β -hCG testing, and will be excluded if pregnancy test is positive. Participants will complete a brief pain assessment, as well as WUR and CPM testing at baseline (Figure 2B). Thereafter, two IV catheters will be inserted in participants' arms. One will be utilized for drug infusion and the catheter in the contralateral arm will be used for serial blood sampling. One 5-ml blood sample will be obtained for P-glycoprotein polymorphism analysis. At study visit 1 and study visit 2, an additional 5-ml baseline blood sample will be obtained for future research with participant consent. Participants will report baseline spontaneous pain (0-10 NRS) and complete a baseline NPSI. Placebo (D5W solution) or tariquidar (4mg/kg dose) will be administered IV over 60 minutes. Starting 30 minutes after the initiation of tariquidar/placebo, a 15-min ondansetron co-infusion will be given, infused via Y-site, to time its peak brain concentration with Pgp inhibition. The intensity of spontaneous pain (on 0-10 NRS) will be assessed every 10 minutes for 60 minutes, and every 15 minutes thereafter for a total of 120 minutes, then every 30 min for a total of 240 minutes. WUR and CPM testing will be repeated 90 minutes after the end of ondansetron infusion (i.e., 105 minutes after the beginning of ondansetron infusion). Participants will record self-reported pain hourly on the study day until bedtime, and daily for 3 weeks thereafter. NPSI pain descriptors will be assessed prior to, and 70 minutes after, the beginning of ondansetron infusion. Additionally, blood samples for ondansetron concentrations will be obtained at baseline (time zero) and approximately at 15, 30, 60, 90, 120, 180, and 240 minutes from the beginning of ondansetron

infusion (See Table 1 for full summary of the measurement schedule.) Plasma will be processed and stored in aliquots at -80°C until analysis. A 3-mL CSF sample (per participant's consent) will be obtained via lumbar puncture between 30 and 180 minutes from the beginning of ondansetron infusion, for the assessment of ondansetron concentration in the CSF using population PK approach as we previously described³¹. Lumbar puncture will not be performed if participant is currently taking anticoagulant treatment or if the participant has a contraindication to the lumbar puncture per investigator discretion.

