2.4.4 Minimization of Bias

There will be no specific ethnic, racial, or gender background for enrollment. The study is designed as cross-over in order to minimize inter-subject variability. The participants and investigators will be blinded to treatment allocation sequence.

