2.4.7 Statistical Methods

All demographic, sensory, analytical and patient-reported data will be captured on case report forms, manually entered to a Research Electronic Data Capture (REDCap) database that will be created for the project, and will be verified by an independent study team member. Plasma and CSF concentrations of ondansetron will be analyzed using a previously validated liquid chromatography method.³⁹ Non-compartmental PK analysis will be performed to construct the concentration-time curves of ondansetron in human plasma with and without tariquidar.³¹ Ondansetron concentration in CSF will be used to evaluate biodistribution of ondansetron to CNS, by the means of CSF to plasma concentration ratio. We do not expect missing outcomes data as all primary and most secondary outcomes will be collected with the participants physically present with the research team. Any missing data will be described, but no data imputation will be attempted. Intergroup comparisons for parametric data will be performed by paired t-test, and for non-parametric data by Wilcoxon signed-rank test for paired samples. McNemar's test will be used to compare paired nominal data, and Fisher's exact test to compare non-paired nominal data.

Sample size:

Change in spontaneous pain reduction (secondary outcome) was used to determine the sample size for the study. The baseline pain intensity (\pm SD) of patients with peripheral neuropathy we have recruited to various studies over the past two years have been 6.3 ± 2.1 . This proof of concept study expects to demonstrate a 30% difference in pain reduction between the two intervention sessions. Given that in a published study of IV ondansetron in NeuP a 20% pain reduction has been observed (although not different from placebo), we assume pain intensity of 5.1 ± 2.1 in ondansetron+placebo group, and expect pain intensity of 4.0 ± 2.1 in ondansetron+tariquidar group at the 60-120 minute timeframe. To determine a significant difference with two-tailed $\alpha < 0.05$ and 85% power (effect size 0.52), 28 subjects will be required in this cross-over study. We expect to enroll 28-32 participants to the study to reach 28 evaluable participants.

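### The between-session pain contrast is a valid change score, but fixing the slope on a single session baseline at 1 is generally less precise than adjusting for that baseline

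*Combined protocol and SAP*

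**What the plan says.** Section 2.4.5.2 item 1 (repeated in the synopsis) names the outcome as "Change in spontaneous pain intensity (measured on 0-10 NRS) from baseline to 60-120 minutes after ondansetron IV infusion, compared between two sessions". For the post-dose side, "The pain severity values obtained at 60, 90, and 120 minutes will be averaged to derive the secondary outcome measure". For the test, "The values will be compared via paired t-test (or Wilcoxon signed-rank test, if data not normally distributed". Section 2.4.7 gives the same general rule: "Intergroup comparisons for parametric data will be performed by paired t-test, and for non-parametric data by Wilcoxon signed-rank test for paired samples". No baseline covariate, analysis of covariance or mixed model is specified for this outcome. Item 2 of 2.4.5.2 also treats NPSI total and sub-scores as changes.

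The baseline is one report per session: "Participants will report baseline spontaneous pain (0-10 NRS) and complete a baseline NPSI" (2.4.3), placed before the tariquidar or placebo infusion. Table 1 lists a further NRS at 0 min. By then tariquidar or placebo has been running for 30 minutes. Nothing says whether that rating counts towards baseline.

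Section 2.4.7 sizes the trial on this secondary outcome, but uses post-dose pain levels: 5.1 with placebo against 4.0 "in ondansetron+tariquidar group at the 60-120 minute timeframe", each with SD 2.1.

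**The concern.** Section 2.4.4 gives the reason for the design: "The study is designed as cross-over in order to minimize inter-subject variability". Comparing the two sessions within a participant already removes that person's stable pain level. A session baseline can then help only by tracking how the person differs from one session day to the other. Subtracting it assumes that a one-point difference in baseline between sessions carries over in full to the post-dose ratings, and it brings all the error of a single 0-10 rating into the contrast. A regression lets the data set the carry-over.

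What is at stake is precision on the outcome that fixed the number of participants. The sizing paragraph makes no allowance for baseline variance, and there is no spare power to absorb a loss (first step of the working).

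**Working it through.** **Inputs.** Difference 5.1 − 4.0 = 1.1, SD 2.1, effect size 0.52, N = 28, two-tailed 0.05 and 85% power, all from 2.4.7. The correlation r is not in the documents. The documents give 2.1 as the SD of pain intensity in a group. Using it as the SD of a within-participant session difference is an assumption, although an effect size of 1.1/2.1 = 0.524 in a paired design implies that use.

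**The plan's own figure.** A paired t-test with effect size 0.52, two-sided 0.05, needs 36 participants for 85% power (35 with 0.524). With 28, power is about 76%. The figure of 28 matches a one-sided 0.05 test, where power is 85.0%. That is a separate matter. It is used here only to show that the design has no slack.

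**Formulas.** For each participant take tariquidar session minus placebo session. Let P be the difference in mean 60-120 minute pain and B the difference in baseline pain, with r = corr(P, B).

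- Change score: Var(P − B) = Var(P) + Var(B) − 2·Cov(P, B). With equal variances V this is 2V(1 − r).
- Adjusted: residual variance V(1 − r²).
- Ratio, change to adjusted: 2(1 − r)/(1 − r²) = 2/(1 + r).
- Ignoring baseline: V. The change score beats this only if 2(1 − r) < 1, that is r > 0.5.

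Power uses the noncentral t distribution: 27 df for the change score, and 26 df for the adjusted intercept, whose standard error is multiplied by √(1 + 1/(n − 3)) for the estimated slope.

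**Example, r = 0.5, SD 2.1 for both P and B.** Change SD = 2.1·√(2 × 0.5) = 2.10, SE = 2.10/√28 = 0.397, noncentrality 1.1/0.397 = 2.77, power 76%. Adjusted SD = 2.1·√0.75 = 1.82, SE = (1.82/√28)·√(1 + 1/25) = 0.351, noncentrality 3.14, power 86%.

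**Case A: SD 2.1 for both P and B**

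| r | Change SD | Change power | Adjusted SD | Adjusted power | Variance ratio |
|---|---|---|---|---|---|
| 0 | 2.97 | 47% | 2.10 | 74% | 2.00 |
| 0.3 | 2.48 | 62% | 2.00 | 78% | 1.54 |
| 0.5 | 2.10 | 76% | 1.82 | 86% | 1.33 |
| 0.7 | 1.63 | 93% | 1.50 | 95.5% | 1.18 |
| 0.9 | 0.94 | about 100% | 0.92 | about 100% | 1.05 |

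Ignoring baseline gives 76% in every row. Simulation with 40,000 trials per r agreed (61.6% against 78.1%, 76.0% against 85.2%, and 93.4% against 95.6% at r = 0.3, 0.5 and 0.7). Simulated type I error was 4.7-5.3% for both methods.

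**Case B: 2.1 is the SD of the difference in changes.** Then V = 2.1²/[2(1 − r)] and the adjusted SD is 2.1·√((1 + r)/2). Change-score power is 76% at every r. Adjusted power:

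| r | Adjusted SD | Adjusted power |
|---|---|---|
| 0.3 | 1.69 | 90% |
| 0.5 | 1.82 | 86% |
| 0.7 | 1.94 | 81% |
| 0.9 | 2.05 | 77% |
| 0.95 | 2.07 | 75.5% |

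**Unequal variances.** The baseline is one rating and the post-dose value averages three, so B may be noisier than P. Hold the SD of P at 2.1 and suppose that session-to-session variance is 20%, 40%, 50% or 60% of a single rating's within-participant variance. Change-score power is then 42%, 64%, 76% and 88%; adjusted power is 78%, 86%, 91% and 96%. Under this model equal SDs understate the loss.

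**The case against.** The strongest reply is that nothing here is wrong. A within-participant change score tested by paired t-test is unbiased and holds its type I error, and the outcome is secondary to pharmacokinetics and tolerability. This stands: the point is one of efficiency. A reader might infer that the planned test is invalid or its estimate biased, and the documents do not support that.

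A reader might also infer that subtracting the baseline is worse than leaving it out. With equal SDs this is true only for r below 0.5. Above that, subtraction helps. Baseline and post-dose ratings are taken hours apart on the same day, while the sessions are about 3 weeks apart, so a high r is plausible and the gain from adjustment could be small. This stands, and is why the tables run to r = 0.9 and beyond.

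The large-sample ratio flatters the adjustment at this size. At r = 0.5 it makes 28 adjusted pairs worth 28 × 1.33 = 37 change-score pairs; after allowing for the estimated slope it is about 35 or 36. Nor is adjustment free in every case. At r = 0.95 in Case B it loses under one point (75.5% against 76%). In the limit where the true slope is exactly 1 the residual SD stays at 2.1, and the cost is 76.2% against 74.4%, just under two points.

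Finally, the sentence on comparing the values, together with sizing on post-dose levels, could be read as a plan to compare post-dose means directly. The outcome is named as a change from baseline, so change is the more natural reading, but the wording should be settled. Under the other reading baseline is not used at all, and adjustment still helps unless r is low.

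**Conclusion.** The concern holds as a point about precision. The change score is valid but generally less precise than adjusting for the session baseline, on the outcome that set N. At r between 0.3 and 0.5 the gain from adjustment is about 9 to 16 points of power if 2.1 is the SD of both session differences, and about 9 to 14 points if 2.1 is the SD of the difference in changes. It shrinks to about 2 to 5 points at r = 0.7 and is negligible by 0.9. Among the values tabulated for r of 0.3 and above, the only loss is under one point, at r = 0.95.

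These figures rest on an assumed r, on 2.1 as a within-participant SD and, in Cases A and B, on equal baseline and post-dose variances. The documents give none of the three, so a reader should not take any single row as the trial's actual loss. The case for changing the plan is the asymmetry: a possibly sizeable gain against a small loss, with data already being collected. For NPSI the same reasoning applies, but no SD or correlation is available and the gain is not quantified.

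**What to change.** In 2.4.5.2 item 1 and the matching synopsis text, make the main analysis a regression of each participant's session difference (tariquidar minus placebo) in mean 60-120 minute pain on the session difference in baseline pain. Report the intercept with its 95% confidence interval as the tariquidar effect.

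Define baseline as the NRS listed as Baseline in Table 1, taken before tariquidar or placebo starts. Exclude the 0-min rating, which treatment may already have affected.

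Keep the paired t-test or Wilcoxon on change as a sensitivity analysis, including for non-normal data, since the regression has no built-in rank counterpart. Apply the same method to NPSI total and sub-scores, using the pre-infusion NPSI.

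The cost is protocol wording and one degree of freedom, with no new data or visits. Make the change before unblinding so that the choice is prespecified.

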2.4 Design and Procedures

2.4.1 Study Design

Randomization and Blinding: The study is designed as a prospective, randomized, double-blind, cross-over experiment in patients with neuropathic pain. After signing informed consent and meeting eligibility criteria, participants will receive two 16 mg IV infusions of ondansetron, approximately 3 weeks apart. Participants will be randomized to the order of tariquidar (4mg/kg dose in 500mL D5W) and placebo (D5W solution) co-administration with ondansetron.

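### The pain comparison ignores period and never estimates a baseline coefficient, and the CPM regression cannot separate a tariquidar response from response common to both sessions

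*Combined protocol and SAP*

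**What the plan says.** **Pain.** Section 2.4.1 gives ondansetron in both sessions ("participants will receive two 16 mg IV infusions of ondansetron") and randomises only what accompanies it: "Participants will be randomized to the order of tariquidar" and placebo. No allocation ratio or blocking is stated. Section 2.4.3 has participants rate spontaneous pain before dosing at each session.

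Item 1 of section 2.4.5.2 is introduced as a change from baseline. It continues "The pain severity values obtained at 60, 90, and 120 minutes will be averaged to derive the secondary outcome measure", and then "The values will be compared via paired t-test (or Wilcoxon signed-rank test, if data not normally distributed". Section 2.4.7 repeats the general rule: "Intergroup comparisons for parametric data will be performed by paired t-test", with the Wilcoxon test as the alternative. The synopsis matches. No section gives a period, sequence or baseline term.

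Section 2.4.7 also says "Change in spontaneous pain reduction (secondary outcome) was used to determine the sample size for the study". The figures used are post-dose intensities: 5.1 with ondansetron plus placebo against 4.0 "in ondansetron+tariquidar group at the 60-120 minute timeframe", both with SD 2.1.

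**CPM.** Item 3 of section 2.4.5.2 regresses percentage pain reduction from baseline on baseline CPM. It takes a significant slope as a sign that analgesic response differs with descending modulation. No session is named. CPM is measured at screening (section 2.4.2) and before dosing at each session (section 2.4.3). The next paragraph of section 2.4.5.2 uses a different outcome, the between-session difference in pain reduction, for sex, weight, wind-up ratio, peak concentration and genotype. That list is open but does not name CPM. Section 2.4.6 treats wind-up ratio as a further stand-in for descending facilitation.

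**The concern.** A crossover that randomises order and records a baseline at each session has the data to remove period effects and to use baseline pain efficiently. The plan does neither. A change score fixes the baseline coefficient at 1 and a post-dose score fixes it at 0. The wording supports both readings, so the power of the planned test depends on which fixed value happens to lie nearer the truth. Pain is a secondary outcome, but it is the one that set the sample size.

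The CPM problem is one of interpretation. Section 2.3 makes psychophysical determinants of response a secondary objective. Every session contains ondansetron and none is drug-free, so a slope within one session mixes response to tariquidar, response to ondansetron and non-specific improvement. The stated rule could turn an association with any of these into a claim about analgesic response. Baseline CPM is also not unique, and the second session's value follows the first treatment.

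**Working it through.** **1. The plan's own figure.** Effect size (5.1 − 4.0)/2.1 = 0.524, stated as 0.52. A paired t-test at two-sided 0.05 and 85% power needs 36 participants with 0.52, or 35 with 0.524. The stated 28 gives 75.6% or 76.2%. A one-sided 0.05 test gives exactly 28. This shortfall is a separate matter from the choice of analysis. It is why the post-dose test below shows 76% and not the stated 85%.

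**2. Baseline coefficient.** Let dY and dB be each participant's tariquidar-minus-placebo differences in post-dose mean and in session baseline. Assume both have SD 2.1, the paired-difference SD implied by the plan's effect size, and correlation b, so that b is also the best coefficient. The SDs are:

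- post-dose: 2.1
- change: 2.1 × √(2(1 − b))
- adjusted: 2.1 × √(1 − b²)

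The documents give no correlations, so b is varied. Power is by simulation at n = 28, 14:14, effect 1.1, two-sided 0.05. The adjusted model regresses dY on sequence and dB.

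| b | SD: change / post-dose / adjusted | Power: change / post-dose / adjusted |
|---|---|---|
| 0 | 2.97 / 2.10 / 2.10 | 47 / 76 / 74% |
| 0.4 | 2.30 / 2.10 / 1.92 | 69 / 76 / 81% |
| 0.6 | 1.88 / 2.10 / 1.68 | 85 / 76 / 90% |

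With a smaller baseline SD (1.6) and baseline between-session correlation 0.6, the best coefficient is 0.98 and power is 95/76/94%. With scores rounded and bounded to 0–10 at b = 0.4, it is 68/76/80%, with type I error 4.8 to 5.0%.

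A grid of 188 admissible correlation sets was also run (same-session baseline–outcome correlation 0.5–0.8, cross-session 0.3–0.5, baseline SD 1.6 or 2.1):

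- adjusted minus change: −2 to +31 points, median +1
- adjusted minus post-dose: −3 to +31 points, median +9
- adjusted minus the better of the two: never below −2.6 points
- change falls up to 33 points below the better test, and post-dose up to 31

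**3. Period effect (size assumed).** At 14:14 and b = 0.4, a 1-point shift in the change gives 62/69/81%. If the shift affects baseline and outcome alike, the figures are 68/68/81%. With unequal sequences the unadjusted estimate is biased by (n₁ − n₂)/N times the period effect. At 16:12 this is (16 − 12)/28 × 1 = 0.14 points, so a true 1.10 is estimated as 0.96 or 1.24. The adjusted estimate stays at 1.10. Section 3.3 replaces withdrawn participants without saying which sequence the replacement takes.

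**4. CPM.** Suppose CPM correlates with response equally in both sessions, so it does not modify the tariquidar effect (n = 28; between-session response correlation 0.5; all assumed).

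| CPM–response correlation | One-session regression significant | Difference regression with sequence term |
|---|---|---|
| 0.3 | 34% | 5% |
| 0.4 | 57% | 5% |
| 0.5 | 80% | 5% |

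The middle column is power for a plain association, but a false-positive rate for a tariquidar-specific claim.

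**5. How much response may be non-specific.** From section 2.4.7, pain is expected to fall 6.3 − 5.1 = 1.2 points with ondansetron alone and 6.3 − 4.0 = 2.3 with tariquidar. The ondansetron-alone figure rests on a study in which "a 20% pain reduction has been observed (although not different from placebo". On that description, up to 1.2/2.3 = 52% of the expected fall in the tariquidar session, and all of it in the other session, may be non-specific.

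**The case against.** A paired test is valid and unbiased with balanced sequences, and the trial is a proof of concept whose primary outcomes are pharmacokinetics and tolerability. Change is the likelier reading: item 1 opens with it, and the 1.1-point difference is the same for change when expected baselines are equal. The median gain over the change score is only about 1 point. The largest gains need baseline pain to predict a score two hours later no better than one three weeks away. In 52% of the grid the gain over change is at most 2 points. Where same-session correlation exceeds cross-session by at least 0.2 (134 scenarios), the median gain is 0.3 and the maximum 14. The documents report no period effect, and sections 2.4.2 and 2.4.3 limit its causes with washout and stable analgesics. All of this stands, and it limits the weight of the first part. It does not settle which value is compared or give a reason to leave the coefficient fixed.

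On CPM, the rule does not mention tariquidar, and sections 2.2 and 2.3 describe an association with pain reduction and determinants of response. As a plain association the regression is legitimate. What remains is that it cannot support a tariquidar-specific claim or separate drug response from non-specific improvement, and that its session and CPM visit are undefined. Differencing sessions also removes any ondansetron effect common to both, so it complements the planned regression and cannot replace it.

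**Conclusion.** The concern holds as a change that should be made, with medium confidence.

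For pain, the issue is mainly precision. The gain from adjustment is often small if change is meant and larger if post-dose scores are meant. Its size depends on correlations the documents do not supply. The case for adjusting is that it never loses more than 2.6 points to the better unadjusted test, while the wrong fixed coefficient can lose more than 30. Bias arises only if sequences end unequal and there is also a period effect on the compared value.

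For CPM, the planned regression is sound as description. Read as evidence that CPM modifies the tariquidar response, it would mislead in 34 to 80% of trials under the assumed common correlations of 0.3 to 0.5.

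**What to change.** 1. **Pain.** For the 60–120 minute mean, regress each participant's tariquidar-minus-placebo difference on sequence coded +0.5/−0.5 (the period term) and on the difference in session baselines. The intercept is the treatment effect. Do the same for NPSI. Keep the paired t-test or Wilcoxon as a sensitivity analysis, and state whether it uses change or post-dose values.
2. **CPM.** Add CPM to the between-session-difference analysis already planned for wind-up ratio and genotype, with a sequence term. Use one CPM value taken before any study drug, and state whether it comes from screening or the first session. Report the slope with its 95% confidence interval. Base any claim that CPM modifies the tariquidar response on this analysis alone. Keep the within-session regression, with its session named, as a descriptive association that may include ondansetron-alone and non-specific response.

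**Cost.** SAP wording only; no new data. The pain model uses two degrees of freedom: about 2 points of power against change if the best coefficient is near 1, and up to 2.6 against post-dose if it is near 0. The CPM difference analysis does not detect an effect common to both sessions. Its power is 34/56/78% when CPM correlates 0.3/0.4/0.5 with the difference, and 80% needs about 0.51. If CPM acts only in the tariquidar session at 0.4, its power is 42/55/81% for between-session response correlations of 0.3/0.5/0.7, against 57% for a tariquidar-session regression. A null result must not be read as absence of modification.

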2.3.2 Inclusion Criteria

1. Age 18-70;
2. Documented diagnosis of neuropathic pain due to damage or disease affecting the peripheral nervous system (e.g. Diabetic neuropathy, Post-herpetic neuralgia, Chemotherapy-induced peripheral neuropathy, Lumbar radiculopathy, or Post-traumatic neuropathy);
3. At least Probable neuropathic pain grading (per Finnerup et al criteria)¹;
4. Pain duration >3 months;

5. Average pain intensity ≥ 4 on 0-10 numerical rating scale (NRS).

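### The CPM regression on % pain reduction has no baseline-pain term and no defined baseline rating; it can lose power, and can give a spurious slope if CPM is related to baseline pain

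*Combined protocol and SAP*

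**What the plan says.** Section 2.4.5.2, item 3 (repeated in the Synopsis under Statistical Methodology), states for baseline CPM magnitude that the association with "the % pain reduction from baseline will be determined by bivariate regression". It then fixes the interpretation: "A significant association between the two measures will be indicative of differential analgesic response as a function of descending pain modulation". Section 2.3 makes psychophysical determinants of response a secondary objective, so a stated aim rests on this model.

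The pieces of the ratio are only partly defined:

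- **Baseline.** Section 2.4.3 says "Participants will report baseline spontaneous pain (0-10 NRS) and complete a baseline NPSI", which reads as one rating on the day. Table 1 shows an NRS at Baseline and another at 0 min, when tariquidar or placebo has been running for 30 minutes. No section says which is the denominator, or that the two are averaged.
- **Post-dose pain.** For item 1, "The pain severity values obtained at 60, 90, and 120 minutes will be averaged to derive the secondary outcome measure". I assume the same average is meant in item 3.
- **Floor.** The minimum of 4 in section 2.3.2 applies to "Average pain intensity" at entry. There is no session-day minimum.
- **Missing values.** Section 2.4.7: "Any missing data will be described, but no data imputation will be attempted". There is no rule for a baseline of 0.

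No section adds baseline pain to the model, says which session supplies the % reduction, or gives power for this regression.

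**The concern.** A % reduction divides by the baseline rating. A one-point error in post-dose pain moves the outcome by 100/3 = 33 percentage points for a patient who starts at 3, and by 100/8 = 12.5 for one who starts at 8. Low or noisy baselines therefore dominate the residual variance, which can hide a real association in a sample of 28.

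The ratio also generally remains correlated with baseline pain. If CPM is related to baseline pain as well, an unadjusted regression passes that link on to the CPM slope. The plan has already committed to reading a significant slope as evidence that descending modulation determines response.

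**Working it through.** **1. The plan's own figure.** The only sample size given (28; two-tailed 0.05; 85% power; effect size 0.52) is for the paired pain comparison, not for this regression. As a two-sided paired t-test it does not reproduce: 36 are needed, and 28 give 75.6% power. That is a separate matter. For the CPM regression, 28 patients give 80% power at a correlation of tanh[(1.96 + 0.84)/√25] = 0.51, so there is little to spare.

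**2. Why % reduction depends on baseline.** From section 2.4.7, baseline pain in patients "recruited to various studies over the past two years have been 6.3 ± 2.1". Assumed post-dose pain is 5.1 ± 2.1 with placebo and 4.0 ± 2.1 with tariquidar. With equal SDs, post = a + r·B + e, where r is the baseline–post correlation (not in the documents) and a = mean post − r × 6.3. Then

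% reduction = 100 × (1 − r − a/B − e/B).

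This is free of B on average only if a = 0, that is r = 5.1/6.3 = 0.81 (placebo) or 4.0/6.3 = 0.63 (tariquidar). In the placebo session a = 1.95 at r = 0.5, 0.69 at r = 0.7 and −0.26 at r = 0.85. The dependence is therefore usual, but its size and sign vary.

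**3. Simulation with CPM tied to the session-day rating.** n = 28, document means and SDs, integer 0–10 ratings, 20,000 trials per cell, two-sided 0.05. The CPM effect is additive, of a size that gives the adjusted model about 80% power. The adjusted model regresses post-dose pain on CPM and baseline.

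Power, CPM unrelated to baseline:

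| r | No session-day floor: planned / adjusted | Floor of 4 on the day: planned / adjusted |
|---|---|---|
| 0.5 | 64.5 / 80.5% | 77.3 / 80.8% |
| 0.7 | 70.8 / 80.7% | 79.4 / 81.1% |
| 0.85 | 74.0 / 80.9% | 79.2 / 80.8% |

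The loss is 7 to 16 points with no floor and 2 to 3.5 with a hard floor of 4.

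Type I error of the planned regression, over all r and floors:

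- CPM–baseline correlation 0: about 5%
- 0.3: 5.2–9.8%
- 0.5: 6.0–18.8%

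The adjusted model stays at 4.7–5.3%.

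**4. Simulation with CPM tied to usual pain and a noisy session rating.** Assumed: usual pain at least 4, a constant 1.9-point effect, residual SD 1.2, rating noise SD 0.5–1.5, and seven pre-dose ratings for the averaged covariate.

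| | Planned % | Adjusted, one rating | Adjusted, mean of seven |
|---|---|---|---|
| Type I error, correlation 0.3–0.5 | 6.2–11.8% | 5.6–24.4% | 4.6–7.2% |
| Power, correlation 0 | 56–81% | – | 82–87% |

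The gap in power between planned and averaged runs from 87 − 81 = 6 points at the least rating noise to 82 − 56 = 26 at the most. I reran this setting and obtained closely similar figures.

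**5. Proportional effect.** Assumed: 12 percentage points per SD of CPM, individual SD 25 points, little rating noise. Power is 57–59% for the planned regression and 55–56% for the adjusted model, so the order reverses slightly.

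**6. Zero baselines.** With ratings distributed as 6.3 ± 2.1 and no floor, about 0.23% are 0, so the chance of at least one in 28 is 1 − (1 − 0.0023)^28 = 6%. If usual pain is at least 4 and day-to-day SD is 0.5–1.5, it is 0–2%.

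**The case against.** The best defence has four parts.

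- **The power loss depends on the generating model.** An additive effect favours adjustment by construction, whereas the plan words its pain effects as percentages. Under a proportional effect with little noise the planned analysis does as well or slightly better, and an entry floor shrinks the loss. This stands: no general power loss can be claimed.
- **The false slope needs a correlation that nobody has reported.** Section 2.4.6 calibrates the CPM test stimulus to each person's own pain level, which gives no reason to expect a strong link with clinical pain. This also stands. A reader might infer that the planned test is invalid or will manufacture a CPM effect; the documents do not support that. Where the correlation is positive, the planned test can even show higher power (81.1% against 77.2% at correlation 0.3, r = 0.5, no floor), though partly through the same baseline link.
- **Simple adjustment can be worse.** If CPM follows usual pain and the covariate is one noisy rating, the adjusted test inflates type I error more than the planned one. This is right, and it decides the form of the remedy. It does not rescue the unadjusted ratio, because averaging several pre-dose ratings largely removes the problem.
- **It is the third secondary outcome of a small proof-of-concept study.** True, and it limits the severity. But the plan states in advance how a significant slope will be read, and the change is cheap.

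**Conclusion.** The point holds in a conditional form. Certain from the text: the regression is unadjusted for baseline pain, the denominator is not fully specified, and no session-day minimum protects it. Conditional: a power loss from about none to about 20 points across most settings (26 in the most extreme), and a false-positive rate above 5% only if CPM is related to baseline pain. The sizes rest on assumptions not in the documents: the baseline–post correlation, rating noise, the form and size of the CPM effect, and the CPM–baseline correlation.

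A reader might also infer that patients will be lost through zero baselines. With entry pain of at least 4 that is unlikely, and it is a minor point. Overall this is a minor-to-moderate weakness in a secondary analysis; pharmacokinetics and tolerability are not touched.

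**What to change.** In section 2.4.5.2, item 3 and the matching Synopsis text:

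1. Make the main analysis a linear regression of absolute post-dose pain (mean of 60, 90 and 120 minutes) on baseline CPM, with baseline pain as covariate. State which session, or which contrast between sessions, is analysed.
2. Define the covariate as the mean of several ratings taken before dosing, for example the daily diary issued at screening plus the session-day baseline. Say whether the 0-min rating counts. Section 2.4.3 allows screening on the morning of test day 1, so also state what is used for patients with few or no diary days.
3. Report the CPM slope with a 95% CI.
4. Keep the regression of % reduction as a supporting analysis, with its denominator defined and a one-line rule for a zero baseline.

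The cost is SAP wording, one degree of freedom and some averaging of ratings that the plan already collects. No new visit or procedure is needed.
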